#### 7. STUDY TREATMENTS

## 7.1. Investigational and Reference Treatments

Study drug in this study includes fasinumab, naproxen, and their matching placebo. Fasinumab and its matching placebo are SC study drug. Naproxen and its matching placebo are oral study drug.

Fasinumab drug product is supplied for this study in the following concentrations:

- Fasinumab 2 mg/mL: Each 1 mL single use pre-filled syringe delivers 0.5 mL of a 2 mg/mL solution (1 mg dose) of study drug
- Fasinumab-matching placebo: Each 1 mL single use pre-filled syringe delivers 0.5 mL of placebo solution

Naproxen 500 mg capsules and naproxen-matching placebo capsules will be provided by the sponsor.

#### Year 1

At the baseline visit of Year 1, patients will be randomized 3:3:3:1 to receive 1 of the following treatment regimens:

- Fasinumab 1 mg SC Q4W and naproxen-matching placebo oral, twice daily
- Fasinumab 1 mg SC Q8W (patients will receive placebo injections at the study visits where study drug is not administered) and naproxen-matching placebo oral, twice daily
- Fasinumab-matching placebo SC Q4W and naproxen 500 mg oral, twice daily
- Fasinumab-matching placebo SC Q4W and naproxen-matching placebo oral, twice daily

All patients will receive SC injections of fasinumab or fasinumab-matching placebo. All SC injections will be in the abdomen, thigh, or upper arm. Patients will be observed in the clinic for approximately 1 hour after study drug is administered. Patients randomized to earlier versions of the protocol with 3 mg Q4W or 6 mg Q8W fasinumab were discontinued from study drug for the remainder of the study and moved directly into the follow-up period.

Naproxen 500 mg or naproxen-matching placebo will be administered orally, twice daily. A proton pump inhibitor or other gastric protective medication may be prescribed if deemed medically necessary by the investigator or sub-investigator.

Doses of SC study drug must be given within  $\pm 7$  days from the scheduled dose date. If the window is missed, the SC dose of fasinumab or fasinumab-matching placebo should not be administered, however the oral dose of naproxen or naproxen-matching placebo will be dispensed. The next SC dose of fasinumab or fasinumab-matching placebo should be administered at the next scheduled dosing date.

Detailed instructions for study drug dose administration are provided in the pharmacy manual.

Year 2

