#### 7.3.2.2. Reasons for Temporary Discontinuation of Study Drug

Study drug may be temporarily discontinued due to medical need, as determined by the investigator. Subcutaneous study drug (fasinumab or fasinumab-matching placebo) will be temporarily withheld while awaiting imaging adjudication for worsening joint pain or when routine imaging suggests adjudicated arthropathy and prompts the need for additional imaging (see Section 9.6.1.1), or for patients who are determined to have orthostatic hypotension or determined to have new or worsening symptoms suggestive of sympathetic nervous system dysfunction while awaiting evaluation by a specialist (see Section 9.6.1.2). Patients may continue to take naproxen or naproxen-matching placebo during this time. Subcutaneous study drug (fasinumab or fasinumab-matching placebo) should not be re-started until the next study visit unless imaging/evaluation results are available within the current visit window. If oral study drug is temporarily discontinued by the investigator, patients may continue to take SC study drug during this time.

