## 10.4.4. Safety Analysis

The summary of safety results will be presented for Year 1, Year 2, and the combined Year 1 and Year 2 treatment periods.

Safety data including TEAEs and treatment emergent AESIs, vital signs, physical exams, laboratory tests, ECGs, and ADA formation will be listed and summarized by treatment group.

Thresholds for potentially clinically significant values (PCSVs) in laboratory parameters and vital signs will be defined by the sponsor and be in effect at the time of final SAP approval.

The time interval to detect any AEs, including AESIs (except JRs identified at the End of Study Phone Calls) is between the first dose of Year 1 study drug injection and the end of Follow-up Period, (either the week 72/Early Termination for those patients not proceeding into Year 2, the week 124E/Early Termination E for those patients proceeding into Year 2, or the Post-Op Joint Replacement Follow-up Visit 2), as well as study drug-related SAEs occurring between the end of Follow-up Period and the End of Study.

For safety variables, the following observation periods are defined:

- The Pretreatment Period is defined as the time from signing the ICF to before the first dose of study drug in Year 1.
- The Year 1 On-Treatment Period is defined as the day from first dose of Year 1 study drug through the day of last Year 1 dose + 4 weeks for those patients not proceeding

into Year 2, or up to the first dose of Year 2 study drug for those patients proceeding into Year 2. Summaries for the Year 1 On-Treatment Period will be based on the SAF – Year 1.

- The Year 1 Post-Treatment Period is defined from the end of the Year 1 On-Treatment Period to the Week 72/Early Termination Visit for those patients not proceeding into Year 2. Summaries for the Year 1 Post-Treatment Period will be based on the SAF Year 1.
- The Year 2 On-Treatment Period is defined as the day from first dose of Year 2 study drug through the day of last Year 2 study drug dose + 4 weeks for those patients proceeding into Year 2. Summaries for the Year 2 Post-Treatment Period will be based on the SAF Year 2.
- The Combined On-Treatment Period is defined as day from first dose of Year 1 study drug through the day of last SC dose + 4 weeks. Summaries for the Combined On-Treatment Period will be based on the SAF Year 1.

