## 5. STATISTICAL METHODS

For continuous variables, descriptive statistics will include the following: the number of patients reflected in the calculation (n), mean, median, standard deviation, minimum & maximum and 1st & 3rd quartiles (Q1 & Q3).

For categorical or ordinal data, frequencies and percentages will be displayed for each category.

**Period of observation** – Unless otherwise stated, analysis of all safety variables captured at multiple visits will be analyzed by the following observations periods:

- The Pre-Treatment Period is defined as the time from signing the ICF to before the first dose of study drug in Year 1.
- The Year 1 On-Treatment Period is defined as the day from first dose of Year 1 study drug through the day of last Year 1 SC dose + 4 weeks for those patients not proceeding into Year 2, or up to the first dose of Year 2 study drug for those patients proceeding into Year 2. Summaries for the Year 1 On-Treatment Period will be based on the SAF – Year 1.
- The Year 1 Post-Treatment Period is defined from the end of the Year 1 On-Treatment Period to the Week 72/Early Termination Visit for those patients not proceeding into Year 2. Summaries for the Year 1 Post-Treatment Period will be based on the SAF – Year 1.
- The Year 2 On-Treatment Period is defined as the day from first dose of Year 2 study drug through the day of last Year 2 SC dose + 4 weeks for those patients proceeding into Year 2. Summaries for the Year 2 On-Treatment Period will be based on the SAF – Year 2.
- The Year 1 and 2 On-Treatment Period is defined as day from first dose of Year 1 study drug through the day of last SC dose + 4 weeks. Summaries for the Year 1 and 2 On-Treatment Period will be based on both the SAF – Year 1 and SAF-Year 2.
- The Year 2 Post-Treatment Period is defined from the end of the Year 2 On-Treatment Period to the Week 124E/Early Termination E Visit for those patients proceeding into Year 2. Summaries for the Year 2 Post-Treatment Period will be based on the SAF – Year 2.

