### 5.8.1. Adverse Events

The verbatim text, the preferred term (PT), and the primary system organ class (SOC) will be displayed in subject listings. Summaries that include frequencies and proportions of patients reporting AEs will include the PTs and the SOCs.

**Pre-treatment AEs** are defined as AEs that developed or worsened during the Pre-Treatment Period.

**Treatment-emergent AEs (TEAEs)** are defined as AEs that developed or worsened during the On-Treatment Periods.

**Post-treatment AEs** are defined as AEs that developed or worsened more than 4 weeks after the last dose of SC study drug.

The focus of adverse event reporting in the clinical study report will be on TEAEs.

For details on handling missing data and partial dates, see Section 6.4.

Summaries of all TEAEs in each treatment group will include:

- Overview of TEAEs, summarizing number of events and number and percentage of patients within the specified category:
  - Total number of TEAEs
  - Total number of serious TEAEs
  - Total number of treatment-emergent AESIs
  - Patients with any TEAEs
  - Patients with any serious TEAEs
  - Patients with any treatment-emergent AESIs
  - Patients with any TEAEs leading to permanent discontinuation from study drug

- Patients with any TEAEs leading to withdrawal from the study
- Patients with any TEAEs leading to death
- TEAEs by SOC and PT
  - All TEAEs
  - TEAEs by severity: mild, moderate or severe
  - TEAEs resulting in permanent study treatment discontinuation
- Study-Drug related TEAEs by SOC and PT
  - All TEAEs
- TEAEs by PT
  - All TEAEs
  - TEAEs resulting in permanent study treatment discontinuation
- Post-treatment AEs by SOC and PT
  - All post-treatment AEs
  - Post-treatment AEs by severity: mild, moderate or severe
- All Serious TEAEs by SOC and PT
- Post-treatment Serious AEs by SOC and PT
- All serious AEs by SOC and PT
- All non-serious TEAEs by SOC and PT
- Post-treatment non-serious AEs by SOC and PT
- All non-serious AEs by SOC and PT
- All AEs by SOC and PT
  - All AEs
  - All AEs by severity: mild, moderate or severe
- Deaths

Counts will be provided according to treatment group for each PT within each SOC. Percentages will be calculated using the number of patients in each treatment group using the respective SAF.

Primary SOC's will be sorted by descending frequency of the 'Fasinumab 1 mg SC Q4W' treatment group. Within each primary SOC, PTs will be sorted by decreasing frequency of investigational product.

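### The SAP ends on-treatment time from the last injection alone, so adverse events on active naproxen can be classed as post-treatment

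*SAP*

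**What the plan says.** SAP Section 5 (period of observation) ends Year 1 "through the day of last Year 1 SC dose + 4 weeks for those patients not proceeding into Year 2" and Year 2 "through the day of last Year 2 SC dose + 4 weeks for those patients proceeding into Year 2". Its combined Year 1 and 2 period is also tied to the last SC dose. SAP 5.8.1 uses the same clock for post-treatment events: "AEs that developed or worsened more than 4 weeks after the last dose of SC study drug". These rules apply to all arms.

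Protocol 10.4.4 is worded differently for the two single-year periods. Year 1 runs "through the day of last Year 1 dose + 4 weeks for those patients not proceeding" into Year 2, in a sentence that opens with the first dose of Year 1 study drug. Year 2 runs "through the day of last Year 2 study drug dose + 4 weeks for those patients proceeding into Year 2". Protocol 7.1 defines study drug as fasinumab, naproxen and their placebos. Only the protocol's Combined period names the injection: "through the day of last SC dose + 4 weeks".

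SAP 1.2.3 states that nothing has been modified from the protocol's statistical section.

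**The concern.** In the naproxen arm the injection is placebo and the capsule is the active drug, so the SAP's clock follows the inactive component. The protocol lets the two separate. When the SC dosing window is missed, the injection is skipped but "the oral dose of naproxen or naproxen-matching placebo will be dispensed" (protocol 7.1). When SC drug is withheld pending joint imaging, adjudication or a specialist's evaluation, "Patients may continue to take naproxen or naproxen-matching placebo during this time" (protocol 7.3.2.2). In either case the SAP period can close while the patient is still taking naproxen.

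Secondary objectives 4 and 5 compare the safety of fasinumab with naproxen, and both documents say that reporting will focus on treatment-emergent events. The on-treatment period also governs the summaries of potentially clinically significant laboratory values and of ECGs, and the classification of concomitant medication. Withholding is prompted by safety findings, so the patients affected need not be a random subset.

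**Working it through.** No stated figure in the plan bears on this, so the check is study-day arithmetic.

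Inputs:
- Schedule days (protocol Table 1): Week 40 = 281, Week 44 = 309, Week 48 = 337, Week 52 = 365, each ±7 days.
- The last scheduled Year 1 injection is at Week 48. Thirteen injections every 28 days from Day 1 give 1 + 12 × 28 = 337, which agrees.
- Assumption: capsules are taken up to the Week 52 visit.

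Formulas:
- SAP end = last SC day + 28.
- End under the protocol's Year 1 wording = last day of any study drug + 28.
- Uncovered naproxen days = max(0, last capsule day − SAP end).

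| Naproxen-arm patient, Year 1 only | Last SC day | SAP end | Last capsule day | Uncovered naproxen days | End under protocol wording |
|---|---|---|---|---|---|
| Exactly on schedule | 337 | 365 | 365 | 0 | 393 |
| Week 48 visit 7 days early, Week 52 visit 7 days late | 330 | 358 | 372 | 14 | 400 |
| Week 48 injection missed or withheld | 309 | 337 | 365 | 28 | 393 |
| Weeks 44 and 48 missed or withheld | 281 | 309 | 365 | 56 | 393 |

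As a share of 365 days, 28 is 7.7% and 56 is 15.3%. Events starting on the uncovered days are post-treatment under the SAP and treatment-emergent under the protocol's wording.

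Year 2 has the same structure. The last scheduled injection is at Week 100E, and 701 + 28 = 729, the Week 104E visit. If that injection is missed, the last is on Day 673, the SAP period closes on Day 701, and 729 − 701 = 28 days are uncovered. Naproxen is taken as needed in Year 2, so these are days on which it may be taken, not days on which it was.

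Under a rule of the later of last SC dose + 28 days and last capsule day, the four Year 1 rows end on Days 365, 372, 365 and 365, with no uncovered naproxen days.

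**The case against.** The strongest reply is that the protocol is not a consistent any-study-drug document. Its Combined period already uses the last SC dose, its adverse-event interval starts at the first injection, and its exposure formula adds 28 days to the last injection because of the biologic's half-life (10.4.4.3). For Year 1 the closing words mention only a dose; study drug has to be read from the start of the sentence. The SAP can fairly be seen as extending one SC anchor to all three periods. This stands to the extent that the protocol also needs reconciling. It does not make SAP 1.2.3 correct, and it does not change which component is active in the naproxen arm.

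The gap is also narrow, and this stands in full. An exactly on-schedule completer has none. Patients who enter Year 2 stay on-treatment in Year 1 until their first Year 2 dose. Permanent discontinuation stops both drugs together (protocol 7.3.2). Nothing is lost from the database: SAP 5.8.1 tabulates post-treatment events, post-treatment serious events and all events. Time to arthropathy is censored at the last visit and time to joint replacement at the last contact, so those analyses do not use this cut-off.

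A full 4-week tail after the last capsule would also be open to challenge. The only stated basis for 28 days is the antibody's half-life, and in the fasinumab arms a placebo capsule would then carry the window to Day 393, 56 days after the Day 337 injection. This argues for a smaller fix, not for leaving the rule alone.

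**Conclusion.** The point holds in limited form. The Year 1 and Year 2 definitions differ between the documents, the SAP does not declare the difference, and its rule can move events on active naproxen into the post-treatment category. The size per patient is 0 days on schedule, up to 14 from slippage, 28 for one missed final injection and 56 for two, assuming capsules to the Week 52 visit.

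Three stronger readings are tempting, and the documents do not support them:
- A reader might infer that naproxen events are undercounted as a fact. They can be. The number of patients affected is not derivable, and a missed late injection shortens the window in the fasinumab arms too, so the net effect between arms is unknown.
- A reader might infer that COVID-19 made the gap likely. Amendment 7 says that travel limits affected receipt of study drug, but capsules are dispensed at the same visits as injections, so a missed visit may have interrupted both.
- A reader might take Day 365 against Day 393 for an on-schedule completer as lost naproxen time. It is a post-dosing tail; no capsule days fall outside the SAP period.

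This should be corrected because it affects the comparator's main safety tables and is cheap to fix. It does not undermine the safety database.

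**What to change.** In SAP Section 5, for all arms and for the Year 1, Year 2 and combined Year 1 and 2 periods alike, end on-treatment time no earlier than the later of (a) last SC dose + 4 weeks and (b) the last oral study drug dose. Patients entering Year 2 keep their existing Year 1 end point. In SAP 5.8.1, start post-treatment events from the same date. The combined period has to be included; otherwise a single-year period could outlast the period that contains it.

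Reconcile the protocol's Year 1, Year 2 and Combined definitions with this rule. Declare any remaining departure in SAP 1.2.3, including whether a 4-week tail applies after the last oral dose.

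The cost is one extra derived date, and the last oral dose date is already needed for the oral compliance formula in SAP 5.6.1. Some events will move from post-treatment to on-treatment in every arm, including the fasinumab arms, where the capsule is placebo. Applying one rule to all arms keeps the comparison symmetric.

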### 5.6.3. Length of Study Observation

The length of study observation is calculated as:

*= (Date of the last study visit [up to the end of the follow-up clinic visit, including post-op joint replacement follow-up visit 2] – date of the first study drug administration in Year 1) + 1*

The total length of study participation is calculated as:

*= (Date of the last scheduled study contact [up to the end of study phone call] – date of the first study drug administration in Year 1) + 1*

The lengths of study observation and participation will be summarized by treatment group using descriptive statistics based on the SAF – Year 1 and SAF – Year 2 separately.

The number and percentage of patients with length of study observation/participation within specific time intervals will be presented by treatment group based on the SAF – Year 1 and SAF – Year 2 separately. The time intervals of interest are specified as:

- For Year 1:  $\geq 1$  day,  $\geq 29$  days,  $\geq 57$  days,  $\geq 85$  days,  $\geq 113$  days,  $\geq 141$  days,  $\geq 169$  days,  $\geq 197$  days,  $\geq 225$  days,  $\geq 253$  days,  $\geq 281$  days,  $\geq 309$  days,  $\geq 337$  days,  $\geq 365$  days,  $\geq 393$  days,  $\geq 505$  days,  $\geq 701$  days.
- For Year 2:  $\geq 365$  days,  $\geq 393$  days,  $\geq 421$  days,  $\geq 449$  days,  $\geq 477$  days,  $\geq 505$  days,  $\geq 533$  days,  $\geq 561$  days,  $\geq 589$  days,  $\geq 617$  days,  $\geq 645$  days,  $\geq 673$  days,  $\geq 701$  days,  $\geq 729$  days,  $\geq 757$  days,  $\geq 869$  days,  $\geq 1065$  days.

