### **5.8. Analysis of Safety Data**

The analysis of safety and tolerability will be performed on the SAF – Year 1 and SAF – Year 2, as defined in Section 3.4.

The safety analysis will be based on the reported AEs and other safety information (clinical laboratory evaluations, vital signs and 12-lead ECG).

Thresholds for Potential Clinically Significant Values (PCSV) in laboratory variables, vital signs and ECG are defined in Section 10.3.

The summary of safety results will be presented for each treatment group and by visit where applicable.

Day 1 is the first day of investigational product, Day –1 is the day before; there is no Day 0.

The time interval to detect any AEs, including AESIs (except JRs identified at the End of Study Phone Calls), or abnormalities is between the first dose of Year 1 study drug dose up to the end of the Follow-Up Period (either the week 72/Early Termination for those patients not proceeding into Year 2, the week 124E/Early Termination E for those patients proceeding into Year 2 or the Post-Op Joint Replacement Follow-up Visit 2). Any study drug-related SAEs occurring between the end of Follow-Up Period and the End of Study will also be included. Data collected outside this interval will be excluded from the descriptive statistics and identification of abnormalities for laboratory evaluations, ECGs and vital signs. All post-baseline data during the interval will be used in the PCSV analysis including scheduled and unscheduled assessments.

All safety analyses will be performed on Year 1 and Year 2 using the following common rules:

- The Year 1 baseline value will be used for all analyses of the Year 1 On-Treatment, Year 1 and 2 On-Treatment and Year 1 Post-Treatment Periods.
- The Year 2 baseline value will be used for all analyses of the Year 2 On-Treatment and Year 2 Post-Treatment Periods.

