A second type of table with counts of each primary SOC in decreasing order of frequency will be provided. A third type of table with counts of each PT in decreasing order of frequency will also be provided.

The above TEAE analyses will be performed for the Year 1 On-Treatment Period, Year 2 On-Treatment Period, Year 1 and 2 On-Treatment Period, Year 1 Post-Treatment Period and Year 2 Post-Treatment Period using the corresponding analyses sets specified in Section 5.

The following listings will be included:

- AEs leading to death
- TEAEs leading to permanent discontinuation from study drug (not applicable to post-treatment AEs)
- TEAEs leading to withdrawal from study
- Patients with Serious TEAEs
- AESIs
- Deaths
- All Cause Joint Replacements
- Pre-treatment AEs
- Post-treatment AEs

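### The Post-Treatment Periods used for the AE tables end before AE detection does, so some post-operative AEs and late drug-related SAEs belong to no period

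*SAP*

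**What the plan says.** The two documents mark the end of AE follow-up in three ways.

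- **Bounded periods.** SAP Section 5 (Period of observation): "The Year 1 Post-Treatment Period is defined from the end of the Year 1 On-Treatment Period to the Week 72/Early Termination Visit for those" patients who stay in Year 1 only. For the others: "The Year 2 Post-Treatment Period is defined from the end of the Year 2 On-Treatment Period to the Week 124E/Early Termination E Visit for" patients who go on to Year 2. Neither definition mentions a joint-replacement (JR) visit, and no later period is defined.
- **A longer detection interval.** SAP 5.8 ends the Follow-Up Period at Week 72/Early Termination, or at "the week 124E/Early Termination E for those patients proceeding into Year 2 or the Post-Op Joint Replacement Follow-up Visit 2". It adds: "Any study drug-related SAEs occurring between the end of Follow-Up Period and the End of Study will also be included". Protocol 10.4.4 has the same interval beside the same bounded periods.
- **An open-ended event class.** SAP 5.8.1 says that post-treatment AEs "are defined as AEs that developed or worsened more than 4 weeks after the last dose of SC study drug", with no end date.

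After listing the AE summaries, SAP 5.8.1 says that they are run for the on-treatment periods and for the "Year 1 Post-Treatment Period and Year 2 Post-Treatment Period using the corresponding analyses sets specified in Section 5".

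The JR follow-up schedule (Protocol Table 3, SAP Table 5) collects AEs through Post-Op Visit 2, 20 weeks after surgery. SAP 5.6.3 measures length of observation "up to the end of the follow-up clinic visit, including post-op joint replacement follow-up visit 2".

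**The concern.** If the tables follow the Section 5 periods, an AE that was deliberately collected after a joint replacement can have a date inside the detection interval but inside no analysis period. The same holds for a drug-related SAE reported after follow-up ends. The plan would count the post-operative weeks as observation time (SAP 5.6.3) while leaving events from those weeks out of the period-based tables.

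This matters more here than in most trials. All-cause joint replacement is a safety endpoint, and JR surgery that meets the criteria in Protocol 9.6.1.4 is an AE of special interest. Protocol 1.1 lists time to total joint replacement among the imbalances behind the decision to stop the higher doses. A table meant to describe what happens after treatment should not be ambiguous about these patients. As the text stands, two programmers could place the same event differently and both cite the SAP.

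**Working it through.** The plan gives no figure to reproduce. The check compares calendar dates.

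**Inputs**

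- Scheduled study days (Protocol Tables 1 and 2; SAP Tables 1 and 2): Week 52 = 365, Week 72 = 505, Week 100 call = 701, Week 104E = 729, Week 124E = 869, Week 152E call = 1065. All satisfy day = 7 × week + 1, for example 7 × 72 + 1 = 505.
- Post-Op Visit 2: follow-up Day 140 (±7) after surgery (SAP Table 5). I take this as surgery day + 140. Counting surgery as Day 1 moves each threshold by one day.
- JR follow-up applies to surgery in the treatment or the follow-up period (Protocol 8.2.3.10).

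**Case 1: patient stays on schedule to Week 72 or 124E**

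For surgery on day S, days outside the period = max(0, S + 140 − E), with E = 505 (Year 1) or 869 (Year 2). The thresholds are 505 − 140 = 365 and 869 − 140 = 729. These are the nominal ends of treatment, because scheduled follow-up and JR follow-up both last 20 weeks. So any surgery during follow-up overshoots.

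| Year 1 surgery day | Post-Op Visit 2 | Days outside | With +7 window |
|---|---|---|---|
| 309 | 449 | 0 | 0 |
| 365 | 505 | 0 | 7 |
| 393 | 533 | 28 | 35 |
| 449 | 589 | 84 | 91 |
| 505 | 645 | 140 | 147 |

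In Year 2, surgery on days 757, 813 and 869 gives the same 28, 84 and 140 days. Even allowing for the window, surgery by day 358 (505 − 147) leaves no gap up to Visit 2.

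**Case 2: drug-related SAEs after follow-up**

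Year 1: 701 − 505 = 196 days (28 weeks). Year 2: 1065 − 869 = 196 days. SAP 5.8 includes these SAEs, but Section 5 has no period for them.

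**Case 3: the pre-operative visit read as the Early Termination visit**

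The schedules of events put Early Termination and JR Pre-operative in one column. If that visit ends the period, the post-operative follow-up of about 140 days (±7) lies outside it. Any part within 4 weeks of the last SC dose remains on-treatment.

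The SAP does not say whether Case 1 or Case 3 applies.

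**The case against.** The strongest reply is that the AE sections already override the bounded periods. Section 5 introduces its periods as a default that other text may displace. SAP 5.8 then sets a longer interval for AEs and says that late related SAEs are included, and SAP 5.8.1 defines post-treatment AEs without an end. The post-treatment tables are named after that event class, and the reference back to Section 5 can be read as concerning only the analysis sets. This reading is available but not secure. The sentence in SAP 5.8.1 names the two Post-Treatment Periods for the AE analyses, and only Section 5 defines them.

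Other parts of the reply limit the point:

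- A reader might infer that these events disappear from the report. The documents do not support that. SAP 5.8.1 plans all-AE and all-serious-AE tables and a listing of post-treatment AEs, and Protocol 10.4.4.1 says that all AEs during the study will be summarised. The all-AE tables are not a certain backstop, because they sit in the same list that is run by period.
- The treatment-emergent tables, the stated focus of reporting, do not use the Post-Treatment Period. Time to adjudicated arthropathy, destructive arthropathy and joint replacement is censored at last visit or last contact, so those analyses are unaffected.
- A reader might infer that every JR patient loses the whole post-operative follow-up. That holds at most under Case 3, and there only beyond 4 weeks after the last SC dose. JR stops study drug, not participation, and the schedule footnotes refer to early termination assessments as applicable. The shared column may therefore be only a list of assessments.
- A reader might also infer a count per arm, or that the loss is greatest in the arm with most replacements. The documents give neither the rate nor the timing of surgery, and in Case 1 timing decides who is affected.

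**Conclusion.** The inconsistency is in the current text of both documents. Read literally, the period-based post-treatment tables omit:

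- AEs between the end of scheduled follow-up and Post-Op Visit 2, for surgery after day 365 (Year 1) or day 729 (Year 2), up to about 140 days per patient;
- drug-related SAEs over the 196 days to the final call;
- under one reading of the combined visit, post-operative follow-up beyond 4 weeks after the last SC dose.

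The day counts assume the nominal schedule. For patients whose Year 2 dosing stopped in August 2020, the calendar days differ but the mismatch is the same. No number of affected patients should be quoted.

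This is a correction that should be made before the tables are programmed. It does not threaten the main safety conclusions.

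**What to change.** In SAP Section 5 and Protocol 10.4.4:

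1. End the Year 1 Post-Treatment Period at the latest of Week 72, Early Termination and Post-Op Joint Replacement Follow-up Visit 2. Do the same for Year 2 with Week 124E and Early Termination E. This is where SAP 5.8 already ends detection.
2. State that, for this analysis definition, a JR pre-operative visit alone does not end the period.
3. State that drug-related SAEs arising after follow-up are counted in the post-treatment serious AE table.

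Protocol 9.4.1, which ends AE recording at Week 72 or 124E/early termination without naming the JR visits, should be reconciled with the JR follow-up schedule.

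The cost is a few lines of text and one changed end date in the AE derivation. The JR schedule already provides for the post-operative data. Post-treatment percentages will rise slightly.
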